The primary aim of this pilot study is to investigate the effect of lower-leg mechanical tactile sensory stimulation on the gait speed and balance function of participants with mild cognitive impairment as measured by the SLUMS Examination. We hypothesize that participants will increase their gait speed and improve clinical outcomes, suggesting less reliance on compensatory executive control⁹ when their Walkasins are turned on.

Pilot Study Design

Research Design

This pilot study will collect data from individuals with mild cognitive impairments who consent to participate in one assessment session. It will employ a pre- and post-test study design to evaluate whether wearing active Walkasins (i.e., Walkasins turned on) improves the participants' gait speed and other clinical outcomes of gait and balance function.

Study Site

The Pillars at Prospect Park, a senior living community located in Minneapolis-St. Paul, has agreed to allow RxFunction to recruit its residents and to use space at its facility to conduct this pilot study. The Pillars will not receive any funds for this project, and its employees will not be engaged in any research-related activities aside from potentially informing prospective participants about the availability of the research, providing prospective participants with the study team's contact information, and/or obtaining the prospective participants' permission for the study team to contact them.

Participant Selection

Up to 20 study participants will be enrolled in this pilot study. To participate, individuals must meet the following inclusion and exclusion criteria.

Inclusion Criteria

- Ambulatory person who is at least 65 years of age
- Ability to understand and provide informed consent: For this study we will assume participants are able to consent if they can satisfactorily answer the following questions:
 - How would you describe your brain health right now?
 - What is this study about?
 - If you decide to be in this study, what harm (risks) might occur?
 - Will this study mainly help you or others?
 - If you want to stop being in the study, when can you do this?
 - Can you please explain how you decided to participate in this study?
- Ability to perceive vibrations from the Walkasins Haptic Module
- Ability to complete the functional outcome measures without the use of an assistive device
- Foot size that allows the Walkasins to function appropriately

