- Mild Cognitive Impairment (MCI) as measured by the Saint Louis University Mental Status (SLUMS) Exam (scores between 20 and 24 + or -2 for those with less than a high school education and scores between 21-26 + or -2 for those who graduated from high school, which indicate mild cognitive impairment) and/or a diagnosis of MCI (or related term) in the person's medical record
- Slow gait speed (<1m/second or slightly faster, provided all other criteria are met)

Exclusion Criteria

- Use of ankle-foot orthosis for ambulation that prevents donning of Walkasins
- Self-reported acute thrombophlebitis including deep vein thrombosis
- Untreated lymphedema
- Untreated lesion of any kind, swelling, infection, inflamed area of skin or eruptions on the lower leg near product use
- Untreated fractures in the foot and ankle
- Self-reported severe peripheral vascular disease
- Other neurological conditions that impact walking (e.g., peripheral neuropathy)
- Weighs more than 300 pounds

Pilot Study Procedures

Specific Training

In addition to completing human subjects research training (e.g., CITI training), the RxFunction study team and any collaborators who assist with the pilot study will receive training on the protocol and procedures as well as their responsibilities and functions prior to their participation in study-related tasks.

Recruitment of Participants

Upon IRB approval of the study, participants may be recruited by flier, personal invitation, and/or referral. Study staff will inform interested individuals about the study and screen individuals for eligibility before inviting them to participate if they are eligible. (See Telephone Screening attachment.)

Consent Procedures

A qualified study team member will conduct the consent discussions in a private space. He/she will provide an overview of the pilot study, its purpose, risks and benefits, etc. Potential participants may take as much time as they need to read the consent form and to ask any questions they may have.

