The final assessment for eligibility is a four-meter timed walk excluding an initial two meters to allow for acceleration. Participants will remain eligible for the pilot study if their gait speed is less than 1m/second. (At their discretion the investigator[s] may enroll individuals whose gait speed is slightly faster than 1m/second, provided they meet all other eligibility criteria.) This test may be repeated if necessary.

[figure not shown]
Participants who meet all eligibility criteria will then don a pair of Walkasins and the PhySens-IMM System. They will perform some brief balance exercises (i.e., sensory integration exercises) and then complete the following assessments with their Walkasins turned off and without the use of an assistive device:

- Short Physical Performance Battery (SPPB): The SPPB “is a composite measure assessing walking speed, standing balance, and sit-to-stand performance.” Research has shown it to be “predictive of an increased risk of falling” among other outcomes associated with older populations.¹² (Complete instructions for the SPPB are available at <https://geriatric toolkit.missouri.edu/SPPB-Score-Tool.pdf>.)
- Timed Up and Go (TUG): The TUG is part of the Centers for Disease Control-recommended STEADI test protocol for balance function.¹³ From a seated position in a standard armchair, the participant is asked to do the following:
 - 1) Stand up from the chair.
 - 2) Walk to a line on the floor 10 feet away normal pace.
 - 3) Turn.
 - 4) Walk back to the chair at normal pace.
 - 5) Sit down again.The tester will record the time taken from the command “Go” until the participant sits down again.
- Timed Up and Go Cognitive (TUG-COG): The TUG-COG is performed as described above; in addition, the participant is asked to count “backwards by threes from a randomly selected number between 20 and 100.”¹⁴ To standardize the assessment for this pilot study, the study team member who conducts the TUG-COG will use the same starting number for all participants (e.g., the same odd number for the first TUG-COG assessment and the same even number for the second TUG-COG assessment).

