- Data collection forms will be reviewed for completeness and consistency. Errors will be corrected, following standard GCP procedures.

Data Sharing

RxFunction may share information from the pilot study with researchers at other companies or institutions in accordance with standard data sharing agreements that

protect the confidentiality of study participants. Only RxFunction company officers may approve data sharing agreements.

Sharing of Results with Participants

At its discretion RxFunction may share information from the study with participants, providing only their own data or via reports summarizing results on all participants if requested (e.g., through a newsletter or RxFunction website posting).

Statistical Analysis Plan

We will use descriptive statistics as well as regression analysis to investigate trends in changes for the various outcomes measured. Walkasins on versus off conditions will be compared using paired t-test as well as Wilcoxon Signed Rank Test for non-normally distributed data. Test of normality will be conducted using the Shapiro–Wilk test. In addition, we may conduct qualitative analyses on participants' comments to answer research questions.

Risks and Potential Benefits

Potential Benefits

There are no direct benefits to individuals who participate in this pilot study; however, we hope that the information gleaned through their participation will enhance our understanding of Walkasins' potential role in the treatment of gait difficulties experienced by individuals with mild cognitive impairments.

Pilot Study Risks and Their Mitigation

- The device being tested may distract the participants while they are walking and increase the risk of falling. To help prevent falling during the testing at the research site, a spotter will walk next to the participants to help them regain balance if a fall starts to occur.
- There is a very low chance that participants may find the device stimulations uncomfortable. If this occurs, the participants can decide if they wish to end participation in the pilot study.
- RxFunction personnel may request participants' medical information relevant to the study, but they will limit the data collected to the minimum necessary to conduct the study.
- There may be other unknown side effects that could occur.

Every effort will also be made to minimize potential risks by the following means:

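### Does the SAP's silence on how gait speed is defined leave the pilot's first hypothesis without an answer?

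*Combined protocol and SAP*

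**What the plan says.** Pilot Study Aim and Hypothesis names gait speed and balance function as the targets, and expects that "participants will increase their gait speed and improve clinical outcomes" with the device on. Research Design sets the comparison out as "gait speed and other clinical outcomes of gait and balance function", in people "who consent to participate in one assessment session".

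Study Visit Procedures has three assessments done after donning with the device off, then repeated with it on: SPPB, TUG and TUG-COG. The SPPB "is a composite measure assessing walking speed, standing balance, and sit-to-stand performance", and its full instructions are given by link. The TUG is written out step by step, including the timing.

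A separate walk comes before donning: "The final assessment for eligibility is a four-meter timed walk excluding an initial two meters to allow for acceleration". Of it the protocol adds: "This test may be repeated if necessary".

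The Statistical Analysis Plan has four sentences. The first is "We will use descriptive statistics as well as regression analysis to investigate trends in changes for the various outcomes measured". The second compares on with off by paired t-test or Wilcoxon signed-rank test. None names an outcome, defines gait speed or says which result leads.

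**The concern.** Gait speed comes first in the hypothesis and is listed apart from the other clinical outcomes, yet the SAP never mentions it. Analysed as three listed totals, the off/on battery gives no gait speed: the SPPB total mixes walking with balance and sit-to-stand, and TUG time includes standing up, turning and sitting down.

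Three harms could follow.

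- If only the SPPB total were kept, a walking effect could be diluted, or a balance effect read as a walking effect.
- If the eligibility walk were used as the off value, choosing slow walkers on that same walk would push the on-minus-off difference upward, in the hypothesised direction.
- With no lead result, a reader might accept whichever outcome looks best.

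There is one visit, and Data Quality rules out imputation of outcomes. A walk time not written down would have to come from another source or be lost.

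**Working it through.** **Figure to reproduce.** None. The documents state no alpha, power, effect size or SD. Apart from the maximum of 20 participants and the 1 m/s threshold, the inputs below are assumptions.

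**Step 1: which passages supply a gait speed off and on?**

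- *SPPB walk.* Done in both conditions, in a test described as assessing walking speed. A speed needs a time over a known distance. This is the natural source.
- *IMU shoe clip.* Donned before the off assessments and removed after the on assessments; results are stored on a card (Description of PhySens IMU Shoe Clip). No speed variable is defined.
- *UWB location system.* Intended as the reference for position and logged to a laptop in real time, at up to 10 Hz. It is not repeated in the visit steps.
- *Eligibility walk.* Done before donning and not among the retested assessments, so it belongs to neither condition.

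The paired comparison in the SAP therefore has a usable gait-speed input. What is unwritten is the sentence connecting the two.

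**Step 2: cost of analysing only the composite.** Assume 20 pairs, two-sided 5%, and a sum of three equally weighted parts with equal SD of change and correlation r. By the noncentral t, walk time has 80% power at a standardised difference d = 0.660.

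If only walking responds, d_comp = d / √(3 + 6r):

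- r = 0: 0.660/√3 = 0.381, power 37%
- r = 0.3: 0.660/√4.8 = 0.301, power 25%
- r = 0.5: 0.660/√6 = 0.270, power 21%

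If all three parts respond equally, d_comp = 3d / √(3 + 6r) = 1.144, 0.904 and 0.809, with power 99.8%, 97% and 93%. The composite is then more powerful than walk time, and what is lost is attribution to gait speed. The hypothesis expects gait speed and other outcomes to improve together, so the case where only walking responds is not the one the plan describes.

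**Step 3: cost of using the eligibility walk as the off value.** Shift from selection = (1 − ICC) · s · φ(a)/Φ(a), with s² = between² + within², 1 − ICC = within²/s² and a = (1.0 − mean)/s. Assume a between-person SD of 0.20 m/s, one trial and a hard cut-off at 1 m/s.

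- Low end (mean 0.9, within-person SD 0.05): s = √0.0425 = 0.206; 1 − ICC = 0.0025/0.0425 = 0.059; a = 0.485; φ/Φ = 0.517; shift = 0.006 m/s.
- High end (mean 1.1, within-person SD 0.10): s = √0.05 = 0.224; 1 − ICC = 0.01/0.05 = 0.20; a = −0.447; φ/Φ = 1.103; shift = 0.049 m/s.

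For scale, the 95% CI half-width at n = 20 is 2.093 × SD/√20, which is 0.047 m/s for an SD of the paired difference of 0.10 (0.023 to 0.070 for SD 0.05 to 0.15). The high-end shift would matter if it arose. But Study Visit Procedures defines off as after donning with the device off, and the SAP compares on with off, so the plan does not use this walk as the off value.

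**Step 4: unranked outcomes.** With three independent tests at an assumed 5% each, the chance of at least one false positive is 1 − 0.95³ = 14.3%. Simulation at n = 20 gives about 14% at correlation 0.3 and 9% at 0.9. This matters if any one positive result were taken as proof of benefit. The SAP speaks of investigating trends, and no confirmatory decision is set out.

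**The case for a change.** The best case for a change is that a short addition would settle the matter. The plan states a directional hypothesis and names tests, so pilot status does not excuse leaving the variable undefined. The most useful product of a pilot is an estimate and SD of the gait-speed change, and that depends on knowing which walk is meant. The protocol tells the tester to record the TUG time but says nothing similar for the SPPB walk, and a single visit allows no second chance.

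Part of this stands. The SAP does not define gait speed, does not choose among the SPPB walk, the IMU and the UWB system, and does not name a lead result. Writing that down would be tidy.

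The recording argument does not stand. The TUG timing appears because the TUG is spelled out; the SPPB timing does not because the SPPB is delegated to a link. That link, the visit flow chart and the data forms are outside the text available, so their content cannot be held against the plan. No passage says that only the total is kept. The claim that an unrecorded time is necessarily lost also overlooks the motion data stored in both conditions, although deriving speed from them would need a definition the protocol does not give.

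**Conclusion.** The omission is real, but it is a gap that analysts fill sensibly. Research Design makes gait speed an outcome, the SPPB supplies a walk in both conditions, and the SAP supplies the paired comparison. Taking these together leads to the on-minus-off difference in SPPB walking speed without contradicting any passage. Gait speed also comes first in the aim, the hypothesis and the design statement, so a reader can tell which result to look at first, with balance function beside it.

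The calculations are arithmetically sound but describe departures from the plan: power of 21% to 37% if only the composite is analysed and only walking responds, and a shift of 0.006 to 0.049 m/s if the eligibility walk is used as the off value. The 14.3% false-positive figure applies only if a single positive result among three were treated as confirmatory, which a pilot of up to 20 people looking for trends does not propose.

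This conclusion assumes that the linked SPPB instructions or the data forms capture walk time and distance. That cannot be confirmed from the documents, and nothing in them suggests otherwise. No change to the plan is needed.
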